| Metagenomic sequencing | X | | X | | |
| Questionnaires¹ | | | | | |
| Risk perception and behavior | X ¹ | | | X | X |
| Socio-economic indicators | X ¹ | | | X | X |
| Use of resources (COVID-19 unrelated) | X ¹ | | | X | X |
| Adverse Events dedicated questionnaire | | X | X | X | X |
| Immune response | | | | | |
| Quantitative Ab anti-S IgG ⁵ | X | X | X | X | X |
| Qualitative Ab anti-N IgM+IgG ⁵ | X | | | | |
| Anti-SARS-CoV-2 sero-neutralization | X | X | X | X | X |
| Cytokine / chemokines | X | X | X | X | X |
| Anti-SARS-CoV-2 cell immunity | | X | | X ⁶ | X ⁶ |

Footnotes

Modular data capture according to level of commitment (level I, level II).

| | |
|----------|---|
| Level I | Assessments in level I are core and should be prioritized |
| Level II | Customized according to the feasibility of each cohort |

*3, 6 and 12 months counted from the 1st dose.

¹For centers able to follow patients since the administration of the first and second vaccination doses the baseline information and the risk perception behavior should be collected at one of these time-points, in the other cases such information should be collected during the first post-vaccination follow-up.

²The assessment at 2nd dose is mandatory in patients who will receive such dose within 8-12 weeks after first dose (current AstraZeneca vaccination schedule).

³If COVID-19 diagnosis, assessments reported in Table 1 are required.

⁴Relevant new medical events or worsening of previous conditions, including new malignancies (type of cancer, overall stage, Kaposi skin-visceral, Lymphoma localization-type, Leukemia lymphoid-myeloid acute-chronic), deep venous thrombosis, pulmonary embolism, infections (including a new SARS-CoV-2-infection during follow-up)

⁵At least one time-point at 1st and 2nd dose is required.

⁶At least one of the three timepoints (month 3, month 6, month 12) is required.

⁷At least one of the four timepoints (2nd dose, month 3, month 6, month 12) is required.

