For patients with a past and/or new diagnosis of SARS-CoV2 infection/COVID-19 disease a pre-established long-term follow-up including multiple diagnostic levels in order to adapt to all the participating cohorts is requested. A detailed overview of the schedule of the study visits and the clinical parameters to be recorded is shown in **Table 1**. Patients who have already had COVID, and new patients being diagnosed with COVID, who can be followed up to at least 12 months, and for whom data can be collected according to **Table 1** should be included. In specific fragile cohorts, such as children cohorts, virtual assessments are allowed.

For patients who have been or will be vaccinated against COVID-19 during the study period, a pre-established monitoring of safety and efficacy in terms of immunological response will be performed. A detailed overview of the schedule of the clinical and laboratory parameters to be recorded is shown in **Table 2**. Patients who have already been vaccinated, or will be vaccinated, who can be followed for 12 months, and for whom data can be collected according to Table 2 should be included. The monitoring should start from the days of first and second dose administration when possible (i.e. vaccination administered in the same center where the patient is followed for the fragile condition), alternatively patients will be monitored at 3±1, 6±2 and 12±3 months after the first vaccination dose.

- Vaccination safety will be assessed by a dedicated questionnaire (Annex 3) distributed to patients at baseline or during the first monitoring visit.

- Vaccination efficacy will be established analyzing the immune response at the predefined time-points. The humoral immune response to vaccination will be assessed by a serological assay able to detect anti-Spike and anti-Nucleocapsid antibodies as well as seroneutralization assays in sera samples. The latter will be useful to exclude possible natural infection at the baseline (1st/2nd dose, or first post-vaccination monitoring visit). The cytokine and cell-mediated immune response to vaccination will be assessed in a subgroup of patients by centralizing samples to a referral laboratory, according to local ethic rules and budget. The number of SARS-CoV-2 paucisymptomatic or symptomatic infection despite vaccination will be also assessed by SARS-CoV-2 detection in respiratory/saliva sample.

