3.2 SAMPLING TIMEPOINTS FOR VACCINATED INDIVIDUALS

3.2.1 Sample collection and management

Vaccinated individuals in WP4 and WP5 will be sampled according to the time points outlined in Table 3. In case of breakthrough infections post vaccination, samples will be collected as outlined in Table 2. Vaccination is (mostly) performed in two doses. Collection is to be performed prior to administration of dose 1 and dose 2, and 3, 6, and 12 months after the first dose (Table 3). Patient inclusion will primarily be based on availability of informed consent for the outlined tasks as well as availability of multiple samples per patient. Informed consent forms should clearly request permission to perform human genetic and epigenetic analyses, without which these analyses cannot be undertaken.

Table 3. Overview sampling and data collection in ORCHESTRA cohorts for vaccinated individuals.

| | 1 st dose | 2 nd dose ¹ | 3 months ² (± 1 month) | 6 months ² (± 2 months) | 12 months ² (± 3 months) | Objective |
|---|----------------------|-----------------------------------|--------------------------------------|---------------------------------------|--|--|
| NP swab | x ³ | x ³ | x ⁴ | x ⁴ | x ⁴ | Viral variant and metagenomic sequencing |
| 2 x 2 mL serum tube (serum) | x | x | x | x | x | Immune - serology and type I IFNs autoantibodies |
| 4 mL EDTA blood tube (plasma) | x | x ⁵ | x ⁵ | x ⁵ | x ⁵ | Immune - cytokine and chemokine |
| 1 (if possible 2) 9 mL heparin tube (PBMCs) | x | x ⁵ | x ⁵ | x ⁵ | x ⁵ | Immune - cellular |
| 2 x 2 mL EDTA tube (whole blood) | x | | x | x | x | Genetic and epigenetic analyses |
| Stool sample (faeces or rectal swab) | x | | x | | | Metagenomic sequencing |

1. The assessment at 2nd dose is mandatory in patients who will receive such dose within 8-12 weeks after first dose (current AstraZeneca vaccination schedule).
2. 3, 6, and 12 months counted from 1st dose.
3. At least one timepoint at 1st or 2nd dose is required.
4. At least one of the three timepoints (month 3, month 6, month 12) is required.
5. At least one of the four timepoints (2nd dose, month 3, month 6, month 12) is required.

| | |
|----------|--|
| Level I | Assessments of Level I are mandatory |
| Level II | Customized according to the feasibility of each cohort |

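### Table 2 gives two schedules for the same cellular assay, and the footnote 7 minimum for cellular and cytokine samples can be met with no sample after dose 2

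*Protocol*

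**What the plan says.** **Cellular and cytokine samples (Protocol 3.2, Table 2).** Two blocks cover the same assays.

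- *Immunology*: the cytokine and cellular rows are both marked at dose 1 and at all four later visits. Footnote 7 requires only one of those four (dose 2, month 3, 6 or 12). Annex 4 Table 3, note 5, repeats this.
- *Immune response*: the cytokine row is marked at all five visits with no footnote. The cell-immunity row is blank at dose 1 and month 3, marked at dose 2, and carries footnote 6 at months 6 and 12. Footnote 6 requires one of months 3, 6 and 12.

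**When the dose-2 sample is drawn (Annex 4, 3.2.1).** "Collection is to be performed prior to administration of dose 1 and dose 2, and 3, 6, and 12 months after the first dose".

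**Time origin (Table 2 footnotes).** Follow-up visits are "3, 6 and 12 months counted from the 1st dose". Footnote 2 makes the dose-2 assessment mandatory for "patients who will receive such dose within 8-12 weeks after first dose".

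**Use of the results (Section 11).** "Vaccination efficacy will be established analyzing the immune response at the predefined time-points". On when sampling begins: "The monitoring should start from the days of first and second dose administration when possible"; "alternatively patients will be monitored at 3±1, 6±2 and 12±3 months after the first vaccination dose". Cytokine and cell-mediated responses are tested in a subgroup only.

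**The concern.** Table 2 decides which tubes a site draws. If its two blocks differ for one assay, sites can follow different rules in good faith, and a sample not drawn cannot be recovered at analysis.

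The footnote 7 minimum matters most. In a two-dose recipient it can be satisfied by a baseline draw and a draw taken just before dose 2. That pair shows the response to one dose and nothing about the full course, although Section 11 rests vaccine efficacy on immune response.

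The time origin adds a smaller problem. Where dose 2 comes late in the 8-12 week range, an early in-window month-3 sample is also a one-dose sample, and the protocol does not say how it is to be labelled.

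**Working it through.** **1. The two cellular schedules side by side (Table 2)**

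| Row | Dose 1 | Dose 2 | Month 3 | Month 6 | Month 12 | Stated minimum |
|---|---|---|---|---|---|---|
| *Immune - cellular* | X | X (fn 7) | X (fn 7) | X (fn 7) | X (fn 7) | one of dose 2, months 3, 6, 12 |
| *Anti-SARS-CoV-2 cell immunity* | blank | X | blank | X (fn 6) | X (fn 6) | one of months 3, 6, 12 |

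The rows disagree on dose 1, on month 3, and on whether the dose-2 draw can be the required follow-up sample. The second row also disagrees with its own footnote, which counts a month the row leaves blank. Footnote 6 does fit the nasopharyngeal-swab row, where all three months carry it.

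**2. A patient sampled only at dose 1 and dose 2**

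- Footnote 7, cytokine and cellular: met, because dose 2 is one of the four.
- Footnote 6, cellular: not met, because none of months 3, 6 and 12 was sampled.
- Post-dose-2 samples obtained: 0, because Annex 4 takes the dose-2 sample before dose 2.

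**3. The cytokine rows.** Both mark the same five visits. They differ only in whether footnote 7's relief applies.

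**4. Month 3 against dose 2.** Inputs: window 3 ± 1 months from dose 1 (Table 2, Section 11); dose 2 at 8-12 weeks (footnote 2); 1 month = 30.44 days (assumption).

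- Window: 2 × 30.44 = day 60.9 to 4 × 30.44 = day 121.8, length 60.9 days; nominal day 91.3.
- Dose 2: 8 × 7 = day 56 to 12 × 7 = day 84.
- Lag from dose 2 to sample: 60.9 − 84 = −23 days to 121.8 − 56 = +66 days. At the nominal day: 91.3 − 84 = 7 to 91.3 − 56 = 35 days.
- Part of the window exposed: 84 − 60.9 = 23.1 days; 23.1 / 60.9 = 38%. A sample from day 84 on cannot precede dose 2.
- Month 6 opens at day 121.8, at least 121.8 − 84 = 38 days after dose 2. Month 12 opens at 9 × 30.44 = day 274, at least 190 days after.

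**5. Share of month-3 samples before dose 2.** Assume dose 2 uniform on days 56-84 (28 days) and independent of the visit day. For visits uniform over a span of length L that opens at day a, with a < 84:

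share = (84 − a)² / (2 × 28 × L)

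| Visit spread | a | L | Share |
|---|---|---|---|
| within ±7 days | 84.3 | 14 | 0% (a is after day 84) |
| within ±14 days | 77.3 | 28 | 6.7² / 1,568 = 2.9% |
| within ±21 days | 70.3 | 42 | 13.7² / 2,352 = 8.0% |
| whole window | 60.9 | 60.9 | 23.1² / 3,410 = about 16% |

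A triangular spread over the whole window, peaking at the nominal day, gives about 8%. The whole-window uniform figure depends on month length: 17% with 30-day months and 25% with 28-day months.

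**The case against.** Much can be said for the plan as it stands.

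- *Labelling samples by dose status is analysis-plan content.* Largely true. The SAP is not shown and may do it. A reader might infer that the protocol pools one-dose and two-dose samples at month 3. It does not say so; it only leaves the possibility open.
- *Counting from dose 1 is coherent.* Accepted. It gives every recipient one origin, including those who never have a second dose.
- *The cytokine rows look like a minimum of two draws against five.* The documents do not support that reading. A plain mark in Table 2 is not a stated minimum: Level I items are to be prioritised and Level II items depend on feasibility. The Level I/II marks did not survive text extraction and may explain part of the difference.
- *Dose dates might be missing.* One might infer this because Section 11 has the Annex 3 form "distributed to patients at baseline or during the first monitoring visit", whereas the Table 2 row "Adverse Events dedicated questionnaire" runs from dose 2 to month 12. But Annex 3 holds both dose dates, Table 2 repeats the form, and Section 14.5 provides monthly requests and queries. A missing date can be filled.
- *Annex 4 yields to the clinical protocol.* That rule cannot settle a conflict between two blocks of Table 2, which is itself in the clinical protocol.

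None of this reconciles the two cellular rows, or closes the route by which footnote 7 is met without a post-dose-2 sample. The subgroup limit in Section 11 does not say which minimum applies within the subgroup.

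**Conclusion.** The point holds and is minor. The firm part needs no assumption about visit timing: Table 2 contains two incompatible cellular schedules, footnote 6 counts a month that the cell-immunity row leaves blank, and footnote 7 can be met for both assays with no result after dose 2. How many patients would be sampled that way cannot be estimated from the protocol.

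The month-3 overlap is possible rather than stated. It concerns only recipients with dose 2 at 8-12 weeks, whose number is not given, and only the first 23 of 61 window days. Under the assumptions in the working the share is 0% to about 3% if visits stay within two weeks of the nominal day, and up to about 16% if they spread evenly over the window. It does not support a claim that the month-3 results are generally unreliable.

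**What to change.** 1. Reconcile the *Immunology* and *Immune response* rows of Table 2, footnotes 6 and 7, and Annex 4 Table 3 note 5 into one minimum for cytokine and cellular samples in the tested subgroup. Under it, a pre-dose-2 draw alone should not count as the follow-up sample in two-dose recipients.
2. Keep the visit calendar. State in Section 11 that immune response is grouped by doses received and days since the last dose at sampling, using the dose dates already on Annex 3.

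The cost is wording and one derived variable. Slightly fewer month-3 samples will count as full-course, and some tested patients may need one later draw.

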4. LIST OF ABBREVIATIONS

AOU – Azienda Ospedaliera-Universitaria
AP-HP - Public Assistance Hospital of Paris
BMI - Body Mass Index
CBCI - Catholics Bishops Conference of India, Society for Medical Education, Bangalore, India
CERMEL - Lambaréné Medical Research Center
CFQ - Cognitive Failure Questionnaire
CFS - Clinical Frailty Scale
CHARITÉ - University Medicine Berlin
CINECA - Interuniversity Consortium
COVID-19 - COronaVirus Disease 19
CRF - Clinical research form
CRO - Clinical Research Associate
CRP C-reactive protein
CTCAE - According to Common Terminology Criteria for Adverse Events
DLCO - Diffusion Lung CO
ECG - Electrocardiograph
eCRF - Electronic clinical research form
EQ-5D-5L - EuroQol five-dimension five-level
EPPICC - European Pregnancy and Paediatric Infections Cohort Collaboration
FEV - Forced Expiratory Volume
FRC – Functional Residual Capacity
FVC - Forced Vital Capacity
GCP - Good Clinical Practice
GMBH German Research Center for Health and Environment
GPAQ - Global Physical Activity, Questionnaire
HADS - Anxiety and Depression Scale
HIV - Human Immunodeficiency Virus
HMGU - Helmholtz Zentrum Muenchen
ICF - Informal Consent Form
ICMJE -International Committee of Medical Journal Editors
ICU - Intensive Care Unit
IES-R - Impact of Event Scale – Revised
INR - International Normalized Ratio
INSERM - Institut National de la Santé et de la Recherche Médicale

INSP - National Institute of Public Health

IQR - Interquartile Range

IRB – Institutional Review Board

IRB/IEC – Institutional review board/independent ethics

IRCCS – Italian scientific health institutions

ISGLOBAL-Barcelona Private Foundation Global Health Institut

K10 - Kessler Psychological Distress Scale

LCTF – Long term care facilities

LIH - Luxembourg Institute of Health

LMU MUENCHEN - Ludwig-Maximilians-University Munich

LTCF – Long Term Care Facilities

mMRC - Modified Medical Research Council

MOS SF - Medical Outcome Study Short Form (MOS SF)-36 Score

MRI - Magnetic Resonance Imaging

PCFS - Post-COVID-19 Functional Status Scale

PCR- polymerase chain reaction

PD – Parkinson Disease

PENTA foundation – for the treatment and care of children with HIV and related diseases - ONLUS

USTUTT - University of Stuttgart

PI – Principal Investigator

RAPH BB - Regional Office of Public Health with its seat in Banská Bystrica

REG VEN-Veneto region

RER-ASSR Emilia Romagna region

RT-PCR - reverse transcriptase–polymerase chain reaction

RV-Residual volume

SAS-Andalusian Health Service

SGRQ - Saint George Respiratory Questionnaire

SoA - Schedule of Assessment

SOFA-Sequential [Sepsis-Related] Organ Failure Assessment Score

TDI - Transition Dyspnoea Index

THSTI - Translational Health Science and Technology Institute, Faridabad, Haryana, India

TLC – Total Lung Capacity

UANTWERPEN - University of Antwerpen

UBA - Universidad de Buenos Aires;

UCD - University College Dublin, Ireland

UHC - Clinic of the University of Cologne

UKHD - Universitätsklinikum Heidelberg, Germany

UMCG - University Medical Center Groningen

UNIBO - University of Bologna

UNIVR - University of Verona

WGS - Whole genome sequencing

WES - Whole exome sequencing

WP - Work Package

5. BACKGROUND

The present study is part of ORCHESTRA project, a three-year international research project aimed at tackling the coronavirus pandemic. ORCHESTRA provides an innovative approach to learn from the pandemic SARS-CoV-2 crisis, derive recommendations to further management of COVID-19 and be prepared for the possible future pandemic waves. The ORCHESTRA project aims to deliver sound scientific evidence for the prevention and treatment of the infections caused by SARS-CoV-2 assessing epidemiological, clinical, microbiological, and genotypic aspects of population, environment and socio-economic features. The project builds upon existing, and new largescale population cohorts in Europe (France, Germany, Spain, Italy, Belgium, Romania, Netherlands, Luxemburg, and Slovakia) and non-European countries (India, Perú, Ecuador, Colombia, Venezuela, Argentina, Brazil, Congo and Gabon) including SARS-CoV-2 infected and non-infected individuals of all ages and conditions. The primary aim of ORCHESTRA is the creation of a new pan-European cohort applying homogenous protocols for data collection, data sharing, sampling, and follow-up, which can rapidly advance the knowledge on the control and management of the COVID-19. ORCHESTRA will include SARS-CoV-2-negative individuals and thereby enable a prospective follow-up and an analysis of vaccination response. The cohort will involve four different populations: general population, COVID-19 patients, fragile individuals (children, elderly, transplanted, oncological, HIV infected, and those with Parkinson disease), and health-care workers. Each of these “perpetual” cohorts can answer different research questions and vaccine strategies. Within the ORCHESTRA project, the Work Package 4 (WP4) will focus on the cohort of fragile patients including children, pregnant women and new-borns, elderly (≥ 65 year age), transplant recipients, cancer patients, patients with HIV infection, and patients with Parkinson Disease.

6. STUDY RATIONALE

Since the beginning of COVID-19 pandemic, several special settings have been identified regarding the susceptibility to SARS-CoV-2 infection, the associated clinical spectrum and outcome. They include pregnant women, pediatric patients, elderly in particular those whole live in long-term care facilities (LTCFs), and immunocompromised hosts including solid organ transplant recipients (SOT), hematopoietic stem cell transplant (HSCT) recipients and patients with cancer.

Among pregnant women and children, asymptomatic or mild diseases have been frequently reported, prompting controversial concerns about their role in the infection transmission in community and hospital settings (1, 2). On the other hand, a high impact of COVID-19 on morbidity and mortality has been described in elderly and immunocompromised hosts (3, 4). Thus, optimization of prevention strategies, screening practices and therapeutic management is strongly advocated in fragile patients (5, 6). Indeed, these settings have been established as priority groups for vaccines. However, safety and efficacy of vaccination in these populations should be careful

assessed. Thus, preliminary epidemiological data are strongly needed to design further intervention trials and health policies.

Besides, an increasing body of evidence suggests that the gut microbiota plays a role in determining the severity of COVID-19, possibly through the modulation of immune responses (8, 9). Furthermore, dysbiosis of the gut microbiota could contribute to the persistence of symptoms, even after the resolution of the disease (10). For the same reasons, the microbiota could be involved in the onset of adverse reactions induced by vaccination, especially in fragile populations, as recently discussed (11). Defining the impact of the microbiota on immunity to vaccination and therefore on its effectiveness is currently considered a priority in various clinical settings (12).

Moreover, early observations show that vaccines do not induce an immune response conferring protection to many fragile patients, resulting in severe Covid-19 cases. It is important to understand what cellular networks and molecular pathways are switched on/off by the administration of vaccines, and to identify the biological patterns that characterize responders and non-responders. DNA methylation and gene expression analyses may inform on the genomic patterns involved in response to vaccines and in the differences between responders and non-responders. Indeed, DNA sequencing may reveal that the perturbation detected at the regulatory levels may be influenced by alterations in the genome of the divergent subjects.

With this premise, we deem that a WP dedicated to fragile patients in the ORCHESTRA project is necessary to inform about the peculiarities of the fragile cohort as a whole, and of each subgroup as well, providing clinical and biological information useful to design targeted prevention and therapeutic strategies.

7. OBJECTIVES

The primary objective of the ORCHESTRA fragile cohorts is to provide an extensive and harmonized collection of epidemiological and clinical data, and biological samples, to assess several features of COVID-19 in each cohort of fragile patients. These include:

- To assess the prevalence of SARS-CoV2 infection and COVID-19 disease in fragile patients;
- To describe the clinical spectrum of COVID-19 disease in different types of fragile patients;
- To analyze epidemiological, clinical and biological predictors of SARS-CoV-2 infection and prognosis in several types of fragile patients;
- To investigate the therapeutic management of COVID-19 and /or of the underlying condition and its impact on the outcome in fragile patients;

- To describe safety and efficacy of COVID-19 vaccination in selected cohorts of fragile patients;
- To describe the relationship between risk perception and adherence to preventive measures over time, including vaccine acceptance;
- To analyze the impact of COVID-19 pandemic on the use of health care services;
- To analyze the socio-economic determinants of infection and disease severity, and the socio-economic impact of the pandemic on cohort specific socio-economic indicators;
- To investigate the psychological consequences of lockdown in fragile patients.
- Identify human genetic markers and epigenetic characteristics in frail patients during post-vaccination monitoring and in the onset of breakthrough infections as well as to analyse the gut microbiome in such patients

